### Brief Summary:

The aim of this study is to quantify the change in 24-hour ambulatory SBP when participants with narcolepsy treated with twice-nightly high-sodium oxybate are transitioned to XYWAV, a low-sodium oxybate. Nonambulatory BP assessments will also be captured during the study. It is hypothesized that there will be a clinically relevant reduction of 24-hour SBP after switching from twice-nightly high-sodium oxybate to XYWAV. The results of this study are anticipated to provide HCPs, patients, and payers with important new information regarding BP changes related to differences in sodium content between available oxybates for the treatment of narcolepsy.

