### **9.3.2. Primary Endpoint**

The primary estimand is described in Section 3. The 24-hour average SBP will be calculated as the average of all ambulatory SBP measurements during the specified 24-hour window.

The primary hypothesis is that the decrease in 24-hour average SBP is statistically significant 6 weeks after switching from twice-nightly high-sodium oxybate to XYWAV.

$$H_0: \Delta_{SBP} = 0; H_1: \Delta_{SBP} < 0$$

$\Delta_{SBP}$  is the difference in the 24-hour average SBP from baseline to EOT, which will be estimated from an analysis of covariance model of the change from baseline as the dependent variable and

mean-centered baseline value as a fixed effect. In addition, 95% confidence intervals will be provided.

Mean centering of baseline values is performed for computational convenience and replaces the observed baseline value in the model ( $X_i$ ) with  $(X_i - X_{\text{mean}})$ , where  $X_{\text{mean}}$  is the estimated mean baseline value in the sample (Barnett, 2005). The resultant model is mathematically equivalent to an “observed value” baseline adjustment model, except that the model intercept term is estimated at the sample mean baseline value rather than at zero.

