## 9.4. Interim Analysis

A 2-stage group sequential design with sample size re-estimation is used for this study. An interim analysis will be performed after 43 participants (75%) have completed the study. This interim analysis will include a binding stopping rule for efficacy if the primary endpoint (specified in Section 3) is met. Using the sample size assumptions described in Section 9.5, the

calculated O'Brien-Fleming alpha level for statistical significance on the primary endpoint is 0.00998 for the interim analysis.

If the primary endpoint does not reach the necessary significance level for early termination at the interim analysis, study enrollment will continue and the final sample size will be adaptively determined using a “promising zone” approach (Mehta, 2011). Based on the observed effect size at the interim analysis, the conditional power (ie, probability of reaching statistical significance at the final analysis given the data obtained at the interim) for the primary endpoint will be calculated. Because the Type I error probability is not inflated when using conditional power and the promising zone methodology used in this study to determine the situations in which the sample size can be increased (Mehta, 2011), no further adjustment to the O'Brien-Fleming boundaries (described in Section 9.1.1) is required for the final analysis.

The conditional power is calculated as follows (Mehta, 2011, equation 6):

$$CP = 1 - \Phi\left(\frac{z_{\alpha}\sqrt{n_2} - z_1\sqrt{n_1}}{\sqrt{\tilde{n}_2}} - \frac{z_1\sqrt{\tilde{n}_2}}{\sqrt{n_1}}\right)$$

Where:

$\Phi(\bullet)$  is the standard normal cumulative distribution function

$n_1$  = actual sample size at interim analysis (expected to be  $n_1 = 43$ )

$n_2$  = planned sample size at final analysis (ie,  $n_2 = 57$ )

$\tilde{n}_2$  = sample size increment between interim and planned final analyses (expected to be  $\tilde{n}_2 = 14$ )

$z_{\alpha}$  = the standard normal value for a type I error rate of  $\alpha$ ; ie,  $\Phi(1 - 0.025) = 1.95996$

$z_1 = \bar{x}_1 / se(\bar{x}_1)$ , the z-statistic for 24-hour SBP change from baseline computed at interim analysis

Based on the calculated conditional power, one of the following 3 actions will be taken:

1. “Favorable zone”: If conditional power  $\geq 90\%$ , continue enrolling participants until the prespecified target sample size ( $N = 57$ ).

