## **1. INTRODUCTION**

The purpose of this statistical analysis plan (SAP) is to describe in detail the statistical methodology and planned analyses to be conducted for Protocol JZP258-406; the current version is based on Protocol v4.0 dated 17 May 2024. Additional analyses or substantial revisions from the analyses outlined in this plan will be documented with rationale in the final CSR.

JZP258-406 is a Phase 3/Phase 4, multicenter, single-arm, open-label switch study. The study will enroll individuals diagnosed with Type 1 or Type 2 narcolepsy [REDACTED].

XYWAV (calcium, magnesium, potassium, and sodium oxybates) oral solution was developed as an alternative, low-sodium formulation of XYREM (high sodium oxybate) and contains the same active moiety, oxybate (GHB), as XYREM. By formulating oxybate with a mixture of cations, XYWAV has 92% less sodium than XYREM in the anticipated dose range of 6 to 9 g nightly.

The aim of this study is to quantify the change in 24-hour average SBP when participants with narcolepsy treated with high-sodium oxybate are transitioned to XYWAV. It is hypothesized that there will be a clinically relevant reduction of SBP after switching from high-sodium oxybate to XYWAV. The results of this study are anticipated to provide healthcare providers, patients, and payers with important new information regarding BP changes related to differences in sodium content between available oxybates for the treatment of narcolepsy.

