### 3.5. Interim Analysis

The interim analysis will be performed after 43 participants (75%) have completed the study. Using the sample size assumptions described in Section 3.3, the calculated O'Brien-Fleming one-sided alpha levels for statistical significance are 0.00998 for the interim analysis and 0.02194 for the final analysis. If the primary endpoint is not rejected at the interim analysis, the final sample size will be adaptively determined based on conditional power.

Conditional power refers to the probability of reaching statistical significance at the final analysis given the data obtained at the interim analysis, and it is calculated according to equation (1):

$$CP = 1 - \Phi\left(\frac{z_{\alpha}\sqrt{n_2} - z_1\sqrt{n_1}}{\sqrt{\tilde{n}_2}} - \frac{z_1\sqrt{\tilde{n}_2}}{\sqrt{n_1}}\right) \quad (1)$$

Where:

$\Phi(\bullet)$  is the standard normal cumulative distribution function

$n_1$  = actual sample size at interim analysis (expected to be  $n_1 = 43$ )

$n_2$  = planned sample size at final analysis (i.e.,  $n_2 = 57$ )

$\tilde{n}_2$  = sample size increment between interim and planned final analyses (expected to be  $\tilde{n}_2 = 14$ )

$z_\alpha$  = the standard normal value for a type I error rate of  $\alpha$ ; i.e.  $\Phi(1-0.025)=1.95996$

$z_1 = \bar{x}_1 / se(\bar{x}_1)$ , the z-statistic for 24-hour SBP change from baseline computed at interim analysis

Given the conditional power, the final sample size target will then be determined using a "promising zone" approach:

- If  $CP \geq 90\%$  (Favorable zone): Continue enrolling more participants until prespecified target sample size ( $N = 57$ ).
- If  $CP < 40\%$  (Unfavorable zone): Continue enrolling more participants until prespecified target sample size ( $N = 57$ ).
- If  $40\% \leq CP < 90\%$  (Promising zone): Calculate additional sample size  $\tilde{n}'_2$  based on formula (2). The final sample size target will be adjusted to  $\min(77, n_1 + \tilde{n}'_2)$ .

$$\tilde{n}'_2 = \left( \frac{n_1}{z_1^2} \right) \left[ \frac{z_\alpha \sqrt{n_2} - z_1 \sqrt{n_1}}{\sqrt{n_2} - \sqrt{n_1}} + z_\beta \right]^2 \quad (2)$$

Where:

$n_1$  = actual sample size at interim analysis (expected to be  $n_1 = 43$ )

$n_2$  = planned sample size at final analysis (i.e.,  $n_2 = 57$ )

$z_\alpha$  = the standard normal value for a type I error rate of  $\alpha$ ; i.e.  $\Phi(1-0.025)=1.95996$

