## 5.4. Level of Significance & Multiplicity Adjustment

To control family-wise error rate inflation due to multiple endpoints and the interim analysis (Section 3.5), a fixed hierarchical testing sequence will be employed. Testing begins with the first endpoint at the specified alpha level and continues through the sequence until an endpoint is not statistically significant. Remaining analyses will be considered exploratory and associated p-values will be considered nominal.

The Type I error rate for study endpoints will be set at a one-sided level of 0.025. To account for the possibility of ending the study at the interim analysis, statistical significance for the primary endpoint (#1) will be assessed using O'Brien-Fleming one-sided alpha levels of 0.00998 for the interim analysis and 0.02194 for the final analysis. Statistical significance for each of the secondary endpoints (#2 to #4) will be assessed using the Pocock one-sided alpha level of 0.0168 at either the interim or final analysis.

Statistical hypotheses to be tested (in sequential order):

1. Change in the 24-hour average SBP (mm Hg) following 6 weeks of XYWAV treatment after switching from high-sodium oxybate in participants with narcolepsy
2. Change in the daytime average SBP (mm Hg) following 6 weeks of XYWAV treatment after switching from high-sodium oxybate in participants with narcolepsy
3. Change in the seated resting average SBP (mm Hg) following 6 weeks of XYWAV treatment after switching from high-sodium oxybate in participants with narcolepsy
4. Change in the nighttime average SBP (mm Hg) following 6 weeks of XYWAV treatment after switching from high-sodium oxybate in participants with narcolepsy

Analyses not part of this hierarchy will be considered exploratory, and no multiplicity adjustment will be performed. P-values reported in standard table outputs will be considered nominal.

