#### **7.1.1. Primary Analysis**

An analysis of covariance (ANCOVA) model will be used to estimate the primary efficacy endpoint using the SAS PROC MIXED procedure on the Completer Set. The model will include the change in 24-hour SBP from baseline to EOT Visit as the dependent variable and the mean-centered baseline 24-hour SBP as an independent variable in the model.

$$\text{BASE\_CENTERED} = \text{BASE} - \overline{\text{BASE}}$$

Example SAS Code for the ANCOVA model is shown below:

```
proc mixed data = DSET;  
  class avisitn;  
  where avisitn = [EOT];  
  model chg = base_centered avisitn;  
  lsmeans avisitn;  
run;
```

Least-squares mean change from baseline (LS-mean), standard error (SE), 95% confidence interval, and *p*-value will be reported. Unadjusted values at each visit, including change from baseline, will also be summarized as continuous variables.

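### The test levels allow for the interim look but the reported mean change and 95% CI do not, which matters modestly for an early-stop report and for borderline secondary endpoints

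*SAP*

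**What the plan says.** Both documents describe the purpose as estimation. Protocol 1.1 (Brief Summary) says "The aim of this study is to quantify the change in 24-hour ambulatory SBP", and the SAP introduction says "The aim of this study is to quantify the change in 24-hour average SBP".

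The design is group sequential. SAP 3.5 states "The interim analysis will be performed after 43 participants (75%) have completed the study", and Protocol 9.4 adds "This interim analysis will include a binding stopping rule for efficacy if the primary endpoint" is met. If the trial does not stop, the target may rise from 57 to at most 77 completers.

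The tests are adjusted for this. In SAP 3.5, "the calculated O'Brien-Fleming one-sided alpha levels for statistical significance are 0.00998 for the interim analysis and 0.02194 for the final analysis". In SAP 5.4, each secondary endpoint "will be assessed using the Pocock one-sided alpha level of 0.0168".

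The estimate and interval are not adjusted. SAP 7.1.1 lists "Least-squares mean change from baseline (LS-mean), standard error (SE), 95% confidence interval" and a p-value from the ANCOVA on the Completer Set. Protocol 9.3.2 says "In addition, 95% confidence intervals will be provided". Protocol 9.3.3 and SAP 7.2.1 carry the same method over to the secondaries. What the documents say about the validity of the adaptive design concerns Type I error only. The sensitivity analyses in SAP 7.1.2 deal with early treatment discontinuation.

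**The concern.** A trial stops at the interim only when the observed fall is large, so the mean reported after a stop is selected upward. The LS-mean is adjusted for baseline but not for this selection. The size of the fall is what the trial promises to clinicians, patients and payers, and at the planned effects an early stop is more likely than not.

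Separately, a two-sided 95% interval corresponds to a one-sided test at 0.025, a level that no endpoint in the hierarchy uses. A table could show an interval that excludes zero beside a test that fails. For a secondary endpoint, that failure also ends formal testing of the endpoints after it.

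**Working it through.** **Inputs.** Interim n = 43, planned N = 57, maximum 77, and one-sided levels 0.00998, 0.02194 and 0.0168 (SAP 3.5 and 5.4; Protocol 9.1.1 and 9.4). Planned falls are 3.0 and 3.5 mm Hg with SD 7.0 to 8.0 (SAP 3.3). Assumptions: the planning SD is taken as the SD of the analysed change. The documents give no number of overruns, so 14 (the step from 43 to 57) is used as an example.

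**1. The plan's own figures reproduce.** A one-sample t-test with the noncentral t gives N = 57 for a fall of 3.5, SD 8 and one-sided 0.025 (power 90.1%). All 18 cells of SAP Table 2 match. Classical two-look O'Brien-Fleming boundaries at information 0.75 give 0.009980 and 0.021936.

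**2. Fall needed to stop.** The standard error at the interim is 8/√43 = 1.220. The critical t at one-sided 0.00998 is 2.419, so a stop needs an observed fall of about 2.419 × 1.220 = 2.95 mm Hg.

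**3. Mean reported fall given a stop.** With known variance, E(fall | stop) = δ + SE × φ(a) / [1 − Φ(a)], where a = 2.327 − δ/SE. For δ = 3.5, a = 2.327 − 2.869 = −0.542 and the result is 4.095. Simulation with an estimated SD (1,000,000 trials per scenario) gives the figures below.

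**4. Overruns.** Overrun participants are not selected by the interim result, so pooling m of them multiplies the bias by 43/(43 + m). For m = 14 the factor is 43/57 = 0.754.

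| SD | True fall | P(stop) | Mean fall given stop | Bias, n = 43 | Bias, 14 overruns pooled |
|---|---|---|---|---|---|
| 8 | 3.5 | 67% | 4.13 | +0.63 | +0.48 |
| 8 | 3.0 | 52% | 3.90 | +0.90 | +0.68 |
| 7 | 3.5 | 80% | 3.86 | +0.36 | +0.27 |
| 7 | 3.0 | 65% | 3.58 | +0.58 | +0.44 |

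**5. Over all outcomes.** With the stop, the promising-zone increase and the final analysis all simulated at SD 8, the average bias is +0.13 at a true 3.5 and +0.14 at 3.0. Coverage of the 95% CI is about 94.8% at both. Coverage given a stop at n = 43 is 96.3% at 3.5 and 95.2% at 3.0.

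**6. Interval against test, primary endpoint, final analysis, SD 8.** At N = 57 the 95% CI excludes zero from an observed fall of 2.12, but significance needs 2.19. At N = 77 the figures are 1.82 and 1.87. The outcome in which the CI excludes zero and the test fails occurs in 0.7% of trials at a true 3.5, 1.1% at 3.0, and at most about 1.7% (near a true 2.0).

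**7. Secondary endpoints.** At N = 57 and SD 8 the figures are 2.12 and 2.31. In normal terms the gap runs from z = 1.960 to z = 2.125. At 80% power the mean of z is 2.125 + 0.842 = 2.967, and P(1.960 < Z < 2.125) = 0.200 − 0.157 = 4.3%. The maximum, with the gap at the centre of the distribution, is about 0.165 × 0.399 = 6.6%.

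**8. Matched levels.** The level is 1 − 2α: 98.0% for 0.00998, 95.6% for 0.02194 and 96.6% for 0.0168. For example, at N = 57 and SD 8 an observed fall of 2.15 has a 95% lower limit of +0.03 and a 95.6% lower limit of −0.03. Only the second agrees with the failed test.

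**9. What a bias-adjusted mean does.** A Whitehead-type mean (fixed 43/57 design, known variance) moves an observed 2.95 to 2.83, 3.50 to 3.39 and 4.13 to 4.06. A conditional correction moves 3.50 to about 1.7 and 4.13 to about 3.6, and it is unstable near the boundary.

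**The case against.** The case for leaving the plan alone is substantial, and most of it stands.

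- Protocol 9.4 and SAP 3.5 already analyse everyone who meets the analysis set criteria, and enrollment is expected to run on during the interim. The n = 43 figures describe the final estimate only if there are no overruns. This stands, so the pooled column belongs beside them.
- Upward bias given a stop is common to designs with an efficacy stop, and the unconditional bias is small. This stands too. It makes the point one of reporting, not of validity.
- Success is defined by p-value thresholds, so no decision is ambiguous. Correct, but the reader of a results table also sees the interval.
- The remedies are imperfect. A Whitehead-type mean shifts the estimate by only about 0.1 mm Hg, and a stage-wise median-unbiased estimate equals the ordinary one at a first-stage stop. A 98.0% interval on pooled data would make matters worse: with 14 overruns it includes zero despite declared success in 1.9% of trials at a true 3.5, against 0.4% for the 95% CI. These limits shape the fix.

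A reader might infer that an early-stopped primary result can carry a CI that contradicts its own test. Without overruns it cannot, because a one-sided p below 0.00998 guarantees that the 95% CI excludes zero. A reader might also infer poor coverage after a stop. At the planned effects coverage is at or above nominal. The poor figure (89%) needs a true fall of 2.0, which is outside the range the plan considers.

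**Conclusion.** The concern holds as a gap in reporting. The plan adjusts its tests for the interim look, while its LS-mean and 95% CI ignore it. At SD 8, given an early stop, the fall is overstated on average by about 0.6 to 0.9 mm Hg at the planned effects with n = 43, or about 0.5 to 0.7 with 14 overruns pooled. Averaged over all outcomes the bias is about 0.1 mm Hg.

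Interval and test disagree in about 4 to 7% of trials for a formally tested secondary with 40 to 80% power, and in at most about 2% for the primary at the final analysis. After an early stop, a primary conflict can arise only through overruns.

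Nothing here shows inflated Type I error or a wrong decision rule. The figures rest on the planning SD. A smaller residual SD after baseline adjustment would reduce the bias, as the SD 7 rows show.

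**What to change.** Add to SAP 7.1.1 and 7.2.1:

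1. Beside the 95% CI, report intervals matched to the test level: 98.0% on the interim dataset that is actually tested, 95.6% for the primary at the final analysis, and 96.6% for secondaries formally tested in the hierarchy. Do not apply the 98.0% level to pooled data that include overruns.
2. Pre-specify one named bias-adjusted mean (for example Whitehead-type) as a supplementary estimate beside the LS-mean. Note that it moves the estimate by only about 0.1 mm Hg and does not remove the bias given a stop.
3. State that after a stop the headline LS-mean uses all Completer Set participants including overruns, as Protocol 9.4 and SAP 3.5 imply. Show the interim estimate as the basis of the test, and footnote that the 95% CI is not adjusted for the interim analysis.

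The cost is SAP wording and a small program. The design and sample size do not change. The downside is slightly wider additional intervals and a slightly less favourable supplementary estimate.

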### 7.1.2. Sensitivity Analyses

To assess the effect of early treatment discontinuation on the endpoint, analyses will be repeated using the Effectiveness Set.

### 7.1.3. Subgroup Analyses

To assess endpoint differences according to potential effect-modifying covariates, additional analyses for subgroups specified in Section 5.5 will be performed using the Completer Set.

Least-squares mean change from baseline (LS-means) and standard error (SE) will be provided for each subgroup. A nominal *p*-value will also be provided. Unadjusted values at each visit for each subgroup, including change from baseline, will also be summarized as continuous variables.

Example SAS Code for the ANCOVA model for subgroup analyses is shown below.

```
proc mixed data = DSET;  
  class SUBG;  
  model chg = base_centered SUBG /s cl;  
  lsmeans SUBG / cl;  
run;
```

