### 1.3. Schedule of Activities

**Table 3: Schedule of Assessments – Site-Based Participants**

Procedure	Screening Period (twice-nightly high-sodium oxybate)	Intervention Period (XYWAV) Telemedicine Visits shaded in gray						E/D	Safety Follow-up Visit	Notes
		Switch to XYWAV					End of Treatment Visit			
Study Visits	V1 a	V2	V3	V4	V5	V6	V7 a		V8	Additional unscheduled visits will be needed a .
Scheduled Day(s)	-14	1	7	14	28	35	42*		56**	*Study intervention to be taken each night until the EOT 24-hour BP assessment has met minimum data quality standards a . **SFU Visit should occur 14 days (+ 3 days) after the last dose of study intervention or E/D Visit (as applicable).
Study Visit Window (days)	-7 (ie, Day -21)		± 3	± 3	± 3	± 3	± 3		+ 3	
Informed consent	X									
Inclusion/exclusion criteria	X	X								Confirm that participant continues to meet eligibility criteria and that screening 24-hour BP measurement meets quality control criteria before switching to XYWAV.
Demographics	X									
Medical history	X									
Physical examination	X									Refer to Section 8.3.1.
Vital signs (OBPM, pulse, height, weight)	X*			X	X		X	X		Triplicate OBPM and pulse rate recordings are collected and averaged automatically using the sponsor-provided device. *At the Screening Visit, triplicate OBPM and pulse rate recordings may be repeated up to 2 additional times (Refer to Section 8.3.2). *Height only required at screening.
Electrocardiogram	X						X	X		
Clinical labs	X									
Serum pregnancy test (WOCBP only)	X									Serum test at screening as assessed by a central laboratory.
Urine pregnancy test (WOCBP only)		X					X	X		Urine tests (dipstick) may be performed at additional study visits, if needed.

Procedure	Screening Period (twice-nightly high-sodium oxybate)	Intervention Period (XYWAV) Telemedicine Visits shaded in gray						E/D	Safety Follow-up Visit	Notes
		Switch to XYWAV					End of Treatment Visit			
Study Visits	V1 a	V2	V3	V4	V5	V6	V7 a		V8	Additional unscheduled visits will be needed a .
Scheduled Day(s)	-14	1	7	14	28	35	42*		56**	*Study intervention to be taken each night until the EOT 24-hour BP assessment has met minimum data quality standards a . **SFU Visit should occur 14 days (+ 3 days) after the last dose of study intervention or E/D Visit (as applicable).
Study Visit Window (days)	-7 (ie, Day -21)		± 3	± 3	± 3	± 3	± 3		+ 3	

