### 2.2.2. Secondary Endpoints

- Change from baseline to EOT Visit on the daytime average SBP (mm Hg)
- Change from baseline to EOT Visit on the seated resting average SBP (mm Hg)
- Change from baseline to EOT visit on nighttime average SBP (mm Hg)

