### 7.2.1. Primary Analysis

The secondary efficacy endpoints will be summarized and analyzed using the Completer Set and methods described for the primary endpoint.

---

As the endpoint is only captured once during follow-up, including the constant-valued visit identifier (AVISITN) as a class covariate will not affect the model while permitting use of the LSMEANS statement to calculate the mean change in SBP.

Daytime and nighttime windows "are best defined using sleeping times reported by individual users' diary cards". Accordingly, day/night windows subdividing the 24-hour ABPM data will be defined using on sleep/wake times captured from participant sleep diary entries on the nights where the ABPM is being used. Sleep diary times may be converted to 12- or 24-hour format as necessary to merge with ABPM entries and perform the summaries. If valid sleep diary entries covering the ABPM night are not available but other diary entries for the visit are available, the weekly mean sleep/wake time (see Section 8.1.3) may be used to create the daytime/nighttime windows (Section 5.2.4).

A supporting analysis of the daytime/nighttime SBP endpoints will be performed using fixed time windows of 09:00h to 21:00h (daytime) and 01:00h to 06:00h (nighttime) for all participants. However, if the percentage of participants with non-missing sleep diary data is below 85% (N<37 at the interim analysis; N<49 to N<66 at the final analysis), then the fixed window analysis will be considered the primary analysis (including use for statistical testing hierarchy) and the diary-based analysis will be considered supportive.

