#### **7.2.3. Subgroup Analyses**

To assess endpoint differences according to potential effect-modifying covariates, additional analyses for subgroups specified in Section 5.5 will be performed using the Completer Set and methods described for the primary endpoint.

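### The example subgroup code in SAP 7.1.3 omits the EOT restriction; run on a multi-visit dataset, it would mix visits and understate standard errors for seated SBP

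*SAP*

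**What the plan says.** The primary code in SAP 7.1.1 runs PROC MIXED on a dataset called DSET and keeps only end-of-treatment records ("where avisitn = [EOT", closing bracket and semicolon following). Footnote 3 explains why a constant visit term is harmless in that code: "As the endpoint is only captured once during follow-up".

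The example code for subgroups in SAP 7.1.3 also runs on DSET. Its model line is "model chg = base_centered SUBG /s cl". The block has no WHERE statement, no visit variable, and no REPEATED, RANDOM or SUBJECT term. The same section adds: "Unadjusted values at each visit for each subgroup, including change from baseline, will also be summarized as continuous variables".

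SAP 7.2.3 carries this to the secondary endpoints: "additional analyses for subgroups specified in Section 5.5 will be performed using the Completer Set and methods described for the primary endpoint". One of those endpoints, in SAP 2.2.2, is "Change from baseline to EOT Visit on the seated resting average SBP (mm Hg".

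In Protocol Table 3 (site-based), the row "Vital signs (OBPM, pulse, height, weight") is marked at Visits 1, 4, 5 and 7 and at early discontinuation. In Protocol Table 4 (decentralized), the corresponding row is marked only at Visits 1 and 7 and at early discontinuation.

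**The concern.** Without a visit restriction or a within-subject term, PROC MIXED treats every record with a non-missing change as an independent observation. For seated SBP, a site-based completer has three scheduled on-treatment records and a decentralized completer has one. Run on a multi-visit DSET, the printed code would have three consequences.

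- **Different quantity.** The site-based LS-mean would average the changes at about Days 14, 28 and 42. The endpoint is the change to EOT.
- **Precision overstated.** Three correlated records from one person would be counted as three people, so the SE and the nominal p-value would be too small.
- **Unequal weight.** Within narcolepsy subtype, baseline antihypertensive use, and any region that mixes the two enrollment routes, each site-based participant would count three times. Where enrollment route is itself the subgroup, site-based is its own level. The fault there is visit mixing and a small SE, with a Day 14/28/42 average set beside a Day 42 value.

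**Working it through.** **Inputs from the documents.** Target of 57 completers, SD of change 8.0 mm Hg and difference 3.5 mm Hg (SAP 3.3); three against one scheduled on-treatment seated-BP records (Protocol Tables 3 and 4).

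**Inputs assumed.** The site-based share s and the residual within-participant correlation of the change, ρ, are not in the documents. I used s from 50% to 100% and ρ of 0.3, 0.5 and 0.7. Applying the SD of 8.0, which was set for 24-hour SBP, to seated SBP is also an assumption, but the SE ratios below do not depend on it.

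**The plan's own figure.** A one-sample t-test on the change, one-sided 0.025, difference 3.5, SD 8.0, gives N = 57 with power 0.9008. The same method matches all 18 cells of SAP Table 2. The plan states no figure for subgroup precision.

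**Record counts and weight.** Records R = 57(3s + 1 − s). Site-based weight w = 3·57s/R.

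- s = 50%: R = 85.5 + 28.5 = 114, w = 85.5/114 = 75%.
- s = 80%: R = 136.8 + 11.4 = 148.2, w = 136.8/148.2 = 92%.
- s = 100%: R = 171, w = 100%.

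**SE ratio.** For a mean of R pooled records, the model reports variance σ²/R. The true variance is σ²[3·57s(1 + 2ρ) + 57(1 − s)]/R². Hence true SE / reported SE = √(1 + 2ρw). The true size of a nominal two-sided 5% test is 2[1 − Φ(1.96/ratio)].

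| s | ρ = 0.3 | ρ = 0.5 | ρ = 0.7 |
|---|---|---|---|
| 50% | 1.204 (size 10.4%) | 1.323 (13.8%) | 1.432 (17.1%) |
| 80% | 1.247 (11.6%) | 1.387 (15.8%) | 1.514 (19.5%) |
| 100% | 1.265 (12.1%) | 1.414 (16.6%) | 1.549 (20.6%) |

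With three records for everyone, the reported SE as a share of the true SE is 1/√1.6 = 79%, 1/√2 = 71% and 1/√2.4 = 65%.

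**Simulation of the printed ANCOVA** (57 participants, SD 8, two subgroups, 2,000 runs per setting, no true change). For s of 60%, 80% and 100%, the unfiltered code rejected in 10% to 21% of runs. At s = 80% and ρ = 0.5, the mean reported SE of a subgroup LS-mean was 0.93 mm Hg against an empirical SD of 1.31. With the EOT restriction restored, the reported SE was about 1.51, the empirical SD was 1.47 to 1.56, and rejection was 4.4% to 5.6%.

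**Shift of the estimate, illustration only.** Suppose the true change is −1.5, −2.5 and −3.5 mm Hg at Visits 4, 5 and 7. The three-visit average for a site-based participant is −2.5. At s = 60% (w = 0.818) the pooled mean is 0.818 × (−2.5) + 0.182 × (−3.5) = −2.68. At s = 80% (w = 0.923) it is −2.58. The EOT value is −3.5. The visit effects are invented to show direction; if the change is already complete by Visit 4, there is no shift.

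**The case against.** The best reply is that the prose already fixes the visit. Seated SBP is defined as a change to EOT, SAP 7.1.3 speaks of differences in the endpoint, and the secondary subgroup analyses follow the primary methods, which restrict to EOT. The code is labelled an example with placeholder names, and DSET is never defined. A programmer working from the prose would filter to EOT. This stands: the documents do not show that visits will be pooled, and a reader who infers a plan to pool Visits 4, 5 and 7 goes further than the text. What remains is that the primary code needs a filter on a dataset of the same name, and SAP 7.1.3 asks for changes at each visit. A multi-visit DSET is therefore the natural reading, and on it the printed code gives the wrong result. SAP 5.2.4 also plans derived last-observed-value records in the analysis datasets, which is a further reason to filter explicitly.

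Other limits also stand:

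- The code is printed under 24-hour SBP. Ambulatory recordings after baseline are scheduled only at Visit 7 or early discontinuation, so in completers the scheduled 24-hour, daytime and nighttime records are single. Of the four tested endpoints, only seated SBP is clearly exposed.
- SAP 5.5 commits to reporting by narcolepsy subtype but says the other subgroup analyses may be done, on key secondary endpoints that it does not define. SAP 7.2.3 says they will be done.
- The model adjusts for baseline, so residual correlation is what matters. Raw changes share one baseline value and correlate more strongly, so a ρ taken from raw changes would overstate the error.
- The subgroup code requests no between-group difference, and the SAP modification history records that subgroup LS-mean differences were removed.

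**Conclusion.** The point holds conditionally and is minor. If the SAP 7.1.3 code is run as printed on a multi-visit dataset, the seated-SBP subgroup LS-means are not changes to EOT. For site-based shares of 50% to 100% and ρ of 0.3 to 0.7, the true SE is 1.20 to 1.55 times the reported SE, and a nominal two-sided 5% test has a true size of about 10% to 21%. Both ranges rest on assumed inputs.

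Two stronger inferences are not supported. First, a reader might conclude that the site-based versus decentralized results are distorted by overweighting. They are not, because route defines the levels; overweighting arises only in subgroups that mix the routes. Participants in the EU are site-based only (Protocol 4.1), so a region confined to the EU is not such a mixture. Second, a reader might think that the trial's main conclusions are at risk. Subgroup p-values are nominal and outside the testing hierarchy, and the main seated-SBP analysis in SAP 7.2.1 uses the primary methods with their EOT restriction. The confirmatory tests, their alpha levels and the target of 57 are unchanged.

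**What to change.** Repeat the EOT WHERE statement of SAP 7.1.1 in the SAP 7.1.3 code, or state that DSET holds exactly one EOT record per participant for these models. Reword footnote 3 so that its single-capture premise covers only the ambulatory endpoints. The by-visit descriptive summaries can stay as they are. The cost is one line of code and one footnote, with no new data, no change to the design and no effect on any confirmatory analysis.
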